4.6.5.9.2. Suicidal Ideation and Behavior Solicited Through C-SSRS

Suicide-related thoughts and behaviors occurring during the entire study period, based on the C-SSRS, will be summarized by treatment group. In particular, for each of the following suicide-related events, the counts and percentages of participants with the event will be summarized by treatment group:

- died by suicide
- nonfatal suicide attempt
- interrupted attempt
- aborted attempt
- preparatory acts or behavior
- active suicidal ideation with specific plan and intent
- active suicidal ideation with some intent to act without specific plan
- active suicidal ideation with any methods (no plan) without intent to act
- nonspecific active suicidal thoughts
- wish to be dead, and
- non-suicidal, self-injurious behavior.

In addition, the counts and percentages of participants who experienced at least 1 of the composite measures will be presented. The participants with at least 1 postbaseline C-SSRS assessment are included. The composite measure is determined at each assessment by the “yes” or “no” responses in the following C-SSRS categories by the study participant:

- Category 1 – Wish to be Dead
- Category 2 – Non-specific Active Suicidal Thoughts

- Category 3 – Active Suicidal Ideation with Any Methods (Not Plan) without Intent to Act
- Category 4 – Active Suicidal Ideation with Some Intent to Act, without Specific Plan
- Category 5 – Active Suicidal Ideation with Specific Plan and Intent
- Category 6 – Preparatory Acts or Behavior
- Category 7 – Aborted Attempt
- Category 8 – Interrupted Attempt
- Category 9 – Actual Attempt (non-fatal), and
- Category 10 – Completed Suicide.

Composite endpoints of suicidal ideation and suicidal behavior based on the above categories are defined below:

- **Suicidal ideation:** A “yes” answer at any time during study to any 1 of the 5 suicidal ideation questions (Categories 1 through 5) on the C-SSRS.
- **Suicidal behavior:** A “yes” answer at any time during study to any 1 of the 5 suicidal behavior questions (Categories 6 through 10) on the C-SSRS.
- **Suicidal ideation or behavior:** A “yes” answer at any time during study to any 1 of the 10 suicidal ideation and behavior questions (Categories 1 through 10) on the C-SSRS.

A listing containing data for each participant with suicidal ideation, suicidal behavior, or nonsuicidal self-injurious behavior during the study by treatment and visit may be provided. Data from all visits are displayed, regardless of a “yes” or “no” answer, for participants with any “yes” answer for suicidal ideation, suicidal behavior, or self-injurious behavior without suicidal intent.

4.6.5.10. Malignancy

Treatment-emergent malignancy will be considered an AESI. The counts and percentages of participants with treatment emergent malignancy will be summarized by treatment and PT and ordered by decreasing frequency. Detailed searching criteria can be found in Appendix 6.6 (Section 6.6).

4.6.5.11. Renal Safety

Laboratory measures related to renal safety will be analyzed as specified for laboratory measurements in Section 4.6.3.6.

Two shift tables examining changes in renal function from baseline to postbaseline will be created. A min-to-min shift table of eGFR estimated by the Chronic Kidney Disease Epidemiology Collaboration (CKD-EPI) equation with units mL/min/1.73 m², using categories (<30, ≥30 to <45, ≥45 to <60, ≥60 to <90, and ≥90 mL/min/1.73m²). A max-to-max shift table of urine albumin-to-creatinine ratio (UACR), using the categories UACR <30 mg/g, 30 mg/g ≤ UACR ≤300 mg/g, UACR >300 mg/g (respectively, these represent normal, microalbuminuria, and macroalbuminuria).

Mixed model repeated measure analyses for eGFR and UACR will be provided. Log transformation will be performed for UACR.

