The C-SSRS should be administered after assessment of adverse events. For this study, the C-SSRS is adapted for the assessment of the ideation and behavior categories only. The Intensity of Ideation and Lethality of Behavior sections are removed.																								
Columbia-Suicide Severity Rating Scale (C-SSRS) (Since Last Visit Version)		X	X	X	X	X	X	X	X	X	X	X	X	X	X	X	X	X	X	X	X	X	X	X
The C-SSRS should be administered after assessment of adverse events and capture information since most recent C-SSRS administration. For this study, the C-SSRS is adapted for the assessment of the ideation and behavior categories only. The Intensity of Ideation and Lethality of Behavior sections are removed.																								
Self-Harm Supplement Form	X	X	X	X	X	X	X	X	X	X	X	X	X	X	X	X	X	X	X	X	X	X	X	X
The Self-Harm Supplement Form should be administered after assessment of adverse events.																								
Self-Harm Follow-up Form	X	X	X	X	X	X	X	X	X	X	X	X	X	X	X	X	X	X	X	X	X	X	X	X
Self-Harm Follow-up Form is only required if triggered by the Self-Harm Supplement Form, per instructions in the form.																								
Laboratory Tests and Sample Collections																								
Hematology	X					X			X													X		X
HbA1c	X		X			X			X			X			X			X			X		X	X

Visit	1	2	3	4	5	6	7	8	9	10	11	12	13	14	15	16	17	18	19	20	21	99	ED	801	
Week of Treatment	-3	-2	0	4	8	12	16	20	24	28	32	36	40	44	48	52	56	60	64	68	72	72			4 wks post end of TxP
Allowable Interval Tolerance (days)		±3	±7	±3	+7	±3	+7	±3	±3	±3	±3	+7	±3	±3	±3	±3	±3	±3	±3	±3	±7	±7			±3
Fasting Visit	X		X	X	X	X	X	X	X			X			X			X			X	X	X	X	X
Telephone Visit										X	X		X	X		X	X		X	X					
Chemistry panel (includes Creatinine for eGFR calculation and glucose)	X		X			X			X			X			X			X			X		X	X	X
	The CKD-EPI equation will be used by the central lab to estimate and report eGFR.																								
Lipid panel	X		X						X														X	X	X
Insulin			X						X														X	X	X
C-peptide			X						X														X	X	X
Free fatty acids	X		X						X														X	X	X
Serum pregnancy	X																								
	For women of childbearing potential only																								
Urine pregnancy (local)			X			X			X			X			X			X				X		X	

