8.3.2.12. Acute Renal Events

Renal safety will be assessed based on repeated renal function assessment as well as assessment of AEs suggestive of acute or worsening of chronic renal failure. Gastrointestinal AEs have been reported with tirzepatide, including nausea, diarrhea, and vomiting. This is consistent with other GLP-1R agonists (Aroda and Ratner 2011). The events may lead to dehydration, which could cause a deterioration in renal function, including acute renal failure. Participants should be advised to notify investigators in case of severe nausea, frequent vomiting, or symptoms of dehydration.

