10.2. Appendix 2: Clinical Laboratory Tests

- The tests detailed below will be performed by a central lab unless designated as local in the SoA and in the table below.
- In circumstances where the sponsor approves local laboratory testing in lieu of central laboratory testing (in the table below), the local laboratory must be qualified in accordance with applicable local regulations.
- Protocol-specific requirements for inclusion or exclusion of participants are detailed in Section 5 of the protocol.
- Additional tests may be performed at any time during the study as determined necessary by the investigator or required by local regulations.
- Pregnancy testing (refer to Section 5.1 Inclusion Criteria for screening pregnancy criteria).
- Investigators must document their review of the laboratory safety results.
- Laboratory results that could unblind the study will not be reported to investigative sites or other blinded personnel and are denoted in the table below.

Clinical Laboratory Tests

Hematology^a	Clinical Chemistry^a
Hemoglobin	Bicarbonate
Hematocrit	Sodium
Erythrocyte count (RBC)	Potassium
Mean cell volume	Total bilirubin
Mean cell hemoglobin concentration	Direct bilirubin
Leukocytes (WBC)	Alkaline phosphatase
Neutrophils, segmented	Alanine aminotransferase (ALT)
Lymphocytes	Aspartate aminotransferase (AST)
Monocytes	Blood urea nitrogen (BUN)
Eosinophils	Creatinine
Basophils	Uric acid
Platelets	Calcium
	Glucose
	Albumin
	Creatine kinase (CK)
Urine Chemistries^a	
Albumin	
Creatinine	
	Hormones (females)
	Pregnancy Test serum ^a and/or urine (local)
	Follicle-stimulating hormone (FSH) ^a
Cystatin-C^a	
HbA1c^a	
Endocrine^a	
Calcitonin	Pancreas (exocrine)^a
Thyroid-stimulating hormone (TSH)	Pancreatic amylase
	Lipase
Nonpharmacogenetic Stored Samples^{a,b}	Immunogenicity^{a,b}
Serum	Anti-tirzepatide antibodies
EDTA plasma	Anti-tirzepatide antibody neutralization
P800 plasma	Pharmacokinetic Sample for Immunogenicity
	Lipid Panel^a
	Triglycerides
	VLDL-C
	HDL-C
	LDL-C ^c
	Total cholesterol
Pharmacogenetics Sample^{a,b}	Calculations^a
Whole blood (EDTA)	eGFR (calculated by CKD-EPI equation)
	UACR

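### The only filtration-rate estimate in the renal safety analysis is creatinine-based, in a trial built to separate the arms on body weight; cystatin C is collected but enters no eGFR

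*SAP*

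**What the plan says.** SAP 4.6.5.11 (Renal Safety) plans "A min-to-min shift table of eGFR estimated by the Chronic Kidney Disease Epidemiology Collaboration (CKD-EPI) equation", with cuts at 30, 45, 60 and 90 mL/min/1.73 m². For albuminuria it plans "A max-to-max shift table of urine albumin-to-creatinine ratio (UACR"). It adds: "Mixed model repeated measure analyses for eGFR and UACR will be provided". The section names the equation but not the filtration marker.

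The protocol supplies the marker. In Section 1.3 the relevant row reads "Chemistry panel (includes Creatinine for eGFR calculation and glucose"), with the note "The CKD-EPI equation will be used by the central lab to estimate and report eGFR". Protocol Appendix 2 (Section 10.2) lists a single calculated eGFR, "eGFR (calculated by CKD-EPI equation").

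Cystatin C has its own row in the Schedule of Activities and is listed as a central laboratory test in Appendix 2. The row carries no subset restriction, whereas the tirzepatide PK row is expressly limited to a subset. Draws fall at Visit 1 and Week 24 and, as the schedule appears to read, at Week 72, early discontinuation and Visit 801 (the last columns are displaced in the text available). The SAP never names cystatin C. It is reached only through a general sentence: "Laboratory measures related to renal safety will be analyzed as specified for laboratory measurements in Section 4.6.3.6".

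Protocol 8.3.2.12 says "Renal safety will be assessed based on repeated renal function assessment", together with adverse events that suggest acute renal failure or worsening chronic renal failure.

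**The concern.** Serum creatinine reflects how much creatinine is produced as well as how fast it is cleared. Production follows muscle mass. If participants on tirzepatide lose more weight and some of that weight is muscle, their creatinine falls with no change in filtration, and creatinine-based eGFR rises. The error would grow with weight lost, so it would differ by arm, and randomization does not remove it. On a safety measure it points in the direction that flatters the active drug.

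At stake is the between-arm reading of the eGFR shift table and mixed model. A gradual fall in filtration on tirzepatide could look smaller than it is, or absent. The marker that could help to detect this is already being collected, but it is never turned into an estimate of filtration.

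**Working it through.** The plan states no figure for this point, so there is nothing to reproduce. The check is textual, followed by an illustration of size.

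**Which marker.** SAP 4.6.5.11 alone does not settle this. Protocol 1.3 ties creatinine to the eGFR calculation, and Appendix 2 lists one calculated eGFR and none from cystatin C. The planned eGFR is therefore creatinine-based.

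**Size of a spurious rise with true filtration unchanged.**

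- From the documents: a planned difference from placebo of at least 11% in body-weight reduction at Week 72 (Protocol 9.2; SAP Section 5).
- Assumed, not in the documents: a 100 kg participant with 55 kg lean mass; 20% to 40% of the extra loss is lean; creatinine is proportional to lean mass; eGFR varies as creatinine to the power −1.2 in the upper creatinine range and about −0.35 in the low range.
- Extra loss: 11% × 100 kg = 11 kg. Lean part: 2.2 to 4.4 kg. Fall in creatinine: 2.2/55 = 4% to 4.4/55 = 8%.
- Upper range: (1/0.96)^1.2 = 1.050 and (1/0.92)^1.2 = 1.105, a rise of about 5% to 10%. At a baseline of 80 that is 80 × 1.050 = 84.0 to 80 × 1.105 = 88.4, or about 4 to 8 mL/min/1.73 m².
- Low range: (1/0.96)^0.35 = 1.014 and (1/0.92)^0.35 = 1.030, a rise of about 1% to 3%.

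**How this could mask a decline.** At steady state, creatinine = generation / GFR. If generation falls by a fraction g and true GFR by a fraction f, creatinine changes by the ratio (1 − g)/(1 − f), and reported eGFR by that ratio to the power −a.

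- With baseline 65 and f = 10%, true GFR is 65 × 0.90 = 58.5, below the SAP cut of 60.
- With g = 5%, which lies inside the 4% to 8% above, the ratio is 0.95/0.90 = 1.056. Reported eGFR is 61.6 for a = 1.0 and 60.9 for a = 1.2. About half the fall is visible, and the participant stays in the 60 to <90 category.
- With g = 10%, which lies outside that range, the ratio is 1 and reported eGFR stays at 65 whatever the exponent.

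**What the other planned renal analyses measure.**

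| Planned analysis | SAP section | Measures filtration rate? |
|---|---|---|
| eGFR shift table and mixed model | 4.6.5.11 | Yes, from creatinine only |
| UACR shift table and mixed model | 4.6.5.11 | No, albumin in urine |
| Acute renal failure and chronic kidney disease searches | 4.6.5.11.1 | No, reported events |
| Dehydration search | 4.6.5.11.2 | No, reported events |
| Generic laboratory summaries, including cystatin C | 4.6.3.6 | Marker level only, no GFR scale |

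**Visits.** Creatinine is drawn at Visits 1 and 3, then at Weeks 12, 24, 36, 48, 60 and 72. Cystatin C has Visit 1, Week 24 and apparently Week 72. Minima taken over such different numbers of draws are not comparable, so a cystatin C min-to-min table set beside the planned one could disagree through sampling frequency alone.

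**The case against.** A reader might infer that renal safety is judged only on creatinine eGFR. The documents do not support that. The SAP also plans UACR analyses, renal and dehydration event searches with severe or serious events as AESIs, and general summaries of renal laboratory measures. Protocol 8.3.2.12 itself pairs renal function tests with adverse events.

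A reader might also infer that cystatin C goes unanalysed. That too is wrong. SAP 4.6.3.6 gives laboratory analytes by-arm summaries by visit, a low/normal/high shift table compared by Fisher's exact test, and a listing of abnormal findings. A rise in cystatin C on tirzepatide could show there. It would not be on a filtration scale or line up with the eGFR categories, and the mixed model in 4.6.3.6 is limited to selected tests that the section does not name.

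The strongest remaining objections are these:

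- The renal risk described in Protocol 8.3.2.12 is acute: gastrointestinal losses, dehydration, then renal failure. The event searches target it directly. A bias that builds slowly with weight loss is not shown to hide it, and the first postbaseline cystatin C draw, at Week 24, comes after the 20-week escalation. This stands. The point concerns gradual decline only.
- The mechanism and its size come from outside the documents. This stands. At the low end, a 1% rise is negligible.
- Cystatin C may itself depend on adiposity, which the drug changes differently by arm. Both estimates could then be biased, and their agreement would not prove renal safety. This stands, and rules out making the conclusion depend on agreement.
- No primary or key secondary claim is affected. SAP 2.1 applies no multiplicity adjustment to safety, and SAP 4.1 allows additional analyses. True, but choosing the filtration marker after unblinding is less credible than naming it beforehand.

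**Conclusion.** The point holds in limited form. The only estimate of filtration rate in the SAP is creatinine-based, and its between-arm comparison may be biased upward in the tirzepatide arms in a trial planned around a weight difference of at least 11%. Cystatin C is scheduled for all participants and enters no eGFR.

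That the eGFR is creatinine-based and cystatin C unused in it comes from the documents. The bias rests on general physiology and on some of the extra loss being muscle. Its size is unknown; about 1% to 10% follows from the assumed lean mass, lean fraction and exponents. A bias of that size could partly mask a gradual decline. The documents do not show that it will, or that an acute renal event would be missed. This is an inexpensive improvement to a safety analysis, not a flaw in the efficacy conclusions.

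**What to change.** In SAP 4.6.5.11:

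1. State that the planned eGFR is creatinine-based, and name the version of the CKD-EPI equation.
2. Add, as a prespecified supportive analysis, CKD-EPI eGFR from cystatin C and from creatinine and cystatin C combined. Report change from baseline by arm and a category shift using the same cuts, at the visits where cystatin C is drawn.
3. Beside these, show creatinine eGFR restricted to the same visits, including Visit 1 as its baseline, so that all versions use the same draws. Keep the planned full-schedule creatinine analyses.
4. Interpret the estimates together. Do not make the renal conclusion depend on their agreement.

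The cost is SAP wording and two derived variables from laboratory data already scheduled. No samples or visits are added, and alpha and the primary analysis are unchanged. The downsides are few time points (Visit 1 as the only baseline, Week 24 as the first postbaseline draw), no information on acute events during dose escalation, and a possible dependence of cystatin C on adiposity. The last should be stated wherever the results are reported.

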4.6.5.11.1. Acute Renal Events

Acute renal events associated with chronic renal failure exacerbation will be captured.

Severe/serious renal events from the SMQ search below will be considered AESIs.

The counts and percentages of participants with acute renal events will be summarized by treatment by using the MedDRA PTs contained in any of the following SMQs:

- Acute renal failure: Narrow terms in Acute renal failure SMQ (20000003) and
- Chronic kidney disease: Narrow terms in Chronic kidney disease SMQ (20000213).

In addition, a listing of participants with treatment-emergent acute renal events may be provided, if deemed necessary.

4.6.5.11.2. Dehydration

Dehydration events will be captured in the Narrow terms in Dehydration SMQ (20000232). Severe/serious dehydration events will be considered AESIs.

The counts and percentages of participants with dehydration will be summarized by treatment and PT and ordered by decreasing frequency. A listing of participants with treatment-emergent dehydration events may be provided, if deemed necessary.

4.6.5.12. Thyroid Safety Monitoring

4.6.5.12.1. Calcitonin

Observed calcitonin data (a thyroid-specific laboratory assessment) will be summarized by treatment and nominal visit.

The counts and percentages of participants with a maximum postbaseline calcitonin value in the following thresholds will be provided by treatment and baseline calcitonin value (≤ 20 ng/L, >20 ng/L to ≤ 35 ng/L, >35 ng/L). Postbaseline: ≤ 20 ng/L, >20 ng/L to ≤ 35 ng/L, >35 ng/L to ≤ 50 ng/L, >50 ng/L to ≤ 100 ng/L, and >100 ng/L.

4.6.5.12.2. C-Cell Hyperplasia and Thyroid Malignancies

Treatment-emergent thyroid malignancies and C-Cell hyperplasia will be considered AESIs. Detailed searching criteria can be found in Appendix 6.6 (Section 6.6).

The counts and percentages of participants with treatment-emergent thyroid C-cell hyperplasia and malignancies will be summarized by treatment and PT ordered with decreasing frequency. In addition, a listing of participants with treatment-emergent thyroid C-cell hyperplasia and neoplasms may be provided if deemed necessary.

4.6.5.13. Treatment-Emergent Arrhythmias and Cardiac Conduction Disorders

Severe/serious treatment-emergent arrhythmias and cardiac conduction disorders will be considered AESIs.

The treatment-emergent arrhythmias and cardiac conduction disorders events will be identified using the MedDRA PTs. Detailed searching criteria can be found in Appendix 6.6 (Section 6.6).

The counts and percentages of participants with treatment-emergent arrhythmias and cardiac conduction disorders will be summarized by treatment and PT nested within SMQ. The PT will be ordered with decreasing frequency within SMQ. A listing of participants with treatment-emergent arrhythmias and cardiac conduction disorders may be provided if deemed necessary.

4.6.5.14. Overdose

Overdose is defined as taking more than 15 mg of tirzepatide in less than 72 hours. Overdosing of tirzepatide will be summarized by treatment group, and a listing of participants with tirzepatide overdosing will be provided.

In addition, a listing of participants reporting AEs related to overdosing of tirzepatide may be provided.

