Study drug dose escalation is double-blinded and will be managed via the interactive web-response system (IWRS). The starting dose is 2.5 mg QW (or matching placebo) for 4 weeks, then the dose is increased by 2.5 mg (or matching placebo) every 4 weeks (2.5 to 5 to 7.5 to 10 mg) for those randomized to 10 mg, continuing to 12.5 to 15 mg for those randomized to 15 mg. The dose is then maintained for the remainder of the study. In participants who experience intolerable GI symptoms, the dose can be changed as described in the Section 6.6.2.

At each of the 8 scheduled telephone visits, procedures will include:

- collection of AEs, PCs, and concomitant medications
- review of SMBG values and hypoglycemic events collected in the diary

- administration of Mental Health questionnaires
- review of participant diary information (to include reinforcement and compliance assessments for study drug administration and lifestyle goals)

Participants should be instructed to contact the investigative site for assistance as soon as possible if they experience any difficulties administering their study medication. Participants should also be advised about the appropriate course of action in the event that study drug is not taken at the required time (late/missing doses).

Study participants will be permitted to use concomitant medications that they require during the study, except certain excluded medications (see Section 5.2) that may interfere with the assessment of efficacy and safety characteristics of the study treatments.

Visit 99

Visit 99 is only applicable to participants who discontinue the study treatment prematurely (before Week 72) and decline to complete the remaining scheduled study visits. These participants will be asked to return for Visit 99 at 72 weeks \pm 7 days after randomization (See Section 7.2.1.). This visit is critical to ensure complete data collection for the primary weight loss endpoint.

Participants should attend this visit in the fasting state. Procedures to be completed are:

- measurement of weight and waist circumference
- listing of concomitant medications
- assessment of AEs, and
- completion of the Mental Health questionnaires (after the AE assessment).

For participants unwilling to attend this visit, their refusal to attend should be documented in the participant medical record.

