6.1. Study Intervention(s) Administered

Arm Name	Tirzepatide 10 mg	Tirzepatide 15 mg	Placebo
Dose	10 mg QW	15 mg QW	N/A
Route of Administration	SC		
Sourcing	Provided centrally by the Sponsor and dispensed via IWRS		
Packaging and Labeling	Study intervention will be provided in autoinjectors (single-dose pens), packaged in cartons to be dispensed. Clinical study materials will be labeled according to country regulatory requirements.		

Abbreviations: IWRS = interactive web-response system; N/A = not applicable, QW = once weekly, SC = subcutaneous.

There are no restrictions on the time of day each weekly dose of study drug is given, but it is advisable to administer the SC injections on the same day and same time each week. The actual date, time, and injection site location of all dose administrations will be recorded in the diary by the participant. If a dose of study drug is missed, the participant should take it as soon as possible unless it is within 72 hours of the next dose, in which case, that dose should be skipped and the next dose should be taken at the appropriate time. The day of weekly administration can be changed if necessary, as long as the last dose was administered 72 or more hours before.

All participants will inject study drug subcutaneously in the abdomen or thigh using the injection supplies provided; a caregiver may administer the injection in the participant's upper arm. The injection site location of all dose administrations will be recorded by the participant. A new autoinjector will be used for each injection. If study drug is to always be injected in the same body region, participants should be advised to rotate injection sites each week.

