7.1.1. Temporary Study Drug Discontinuation

In certain situations, after randomization, the investigator may need to temporarily interrupt study drug. Every effort should be made by the investigator to maintain participants on study drug and to restart study drug after any temporary interruption, as soon as it is safe to do so. Distribution of study medication at the correct dose will be per IWRS instructions.

If study drug interruption is...	then...
2 consecutive doses or less	participant restarts study drug at last administered dose, as per escalation schedule.
3 consecutive doses or more	participant restarts study drug (at 5 mg, managed by IWRS) and repeats dose escalation scheme.
due to an AE	the event is to be documented and followed according to the procedures in Section 8.3 of this protocol.
due to intolerable persistent GI AE	participants should be treated as suggested in Section 6.6.2.

Abbreviations: AE = adverse event; GI = gastrointestinal; IWRS = interactive web response service.

Investigators should inform the sponsor that study drug has been temporarily interrupted. The data related to temporary interruption of study treatment will be documented in source documents and entered on the eCRF.

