8.4. Treatment of Overdose

Study drug overdose (more than the specified number of injections) will be reported as an AE. In the event of overdose, refer to the IB for tirzepatide.

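### The SAP's overdose summary counts only more than 15 mg of tirzepatide in under 72 hours, so it omits double injections at 2.5, 5 and 7.5 mg and every extra placebo injection, which the protocol treats as overdose (minor)

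*SAP*

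**What the plan says.** Protocol section 8.4 gives the reporting rule: "Study drug overdose (more than the specified number of injections) will be reported as an AE". It sets no amount in milligrams and no time window, and it refers to study drug, which covers placebo as well as tirzepatide.

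SAP section 4.6.5.14 gives the analysis rule: "Overdose is defined as taking more than 15 mg of tirzepatide in less than 72 hours". It then states what is built on it: "Overdosing of tirzepatide will be summarized by treatment group, and a listing of participants with tirzepatide overdosing will be provided". A further listing of adverse events related to overdosing of tirzepatide is optional.

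The dosing schedule is in Protocol section 4.1.1.2.2: "The starting dose is 2.5 mg QW (or matching placebo) for 4 weeks", then increases of 2.5 mg every 4 weeks until 10 mg or 15 mg is reached. Protocol section 6.1 makes the injection the natural unit of count: "A new autoinjector will be used for each injection". Under Protocol section 7.1.1, after 3 or more consecutive missed doses the "participant restarts study drug (at 5 mg, managed by IWRS) and repeats dose escalation scheme".

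**The concern.** The same word names two different events. The protocol counts injections. The SAP counts milligrams against a threshold equal to the highest study dose. One extra pen is therefore in or out of the overdose summary depending only on the dose step the participant has reached, and it is always out on placebo.

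What is at stake is how the overdose summary and listing are read. Someone who knows the protocol's definition would take the table as a full count of overdoses by arm. It would in fact leave out the most direct form of the event, a doubled weekly dose, during the low steps of escalation. Protocol section 4.3 says that slow escalation is meant to allow time for gastrointestinal tolerance to develop, so this is a period in which a reader may well look for such events. The placebo column would show a zero that says nothing about how often placebo participants injected twice.

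**Working it through.** No power, sample-size or alpha figure bears on this point, and the SAP threshold is a definition, so there is no derived figure to reproduce. The check is direct arithmetic.

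**Inputs**
- Threshold: total tirzepatide strictly more than 15 mg in less than 72 hours (SAP 4.6.5.14).
- Dose steps, d: 2.5, 5, 7.5 and 10 mg in both active arms, then 12.5 and 15 mg in the 15 mg arm, with 4 weeks at each escalation step (Protocol 4.1.1.2.2).
- Placebo: 0 mg of tirzepatide per injection.
- Treatment period: 72 weeks.

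**Formulas**
- A double injection inside the window counts under the SAP if 2 × d > 15, that is, if d > 7.5.
- The smallest number of injections that exceeds 15 mg is k = floor(15 / d) + 1.

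| Step d (mg) | 2 × d (mg) | Overdose under Protocol 8.4? | Counted under SAP 4.6.5.14? | k |
|---|---|---|---|---|
| 0 (placebo) | 0 | yes | no | none |
| 2.5 | 5 | yes | no | 7 |
| 5 | 10 | yes | no | 4 |
| 7.5 | 15 | yes | no | 3 |
| 10 | 20 | yes | yes | 2 |
| 12.5 | 25 | yes | yes | 2 |
| 15 | 30 | yes | yes | 2 |

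The 7.5 mg row turns on the strict inequality: 15 is not more than 15. Had the rule been 15 mg or more, that row would count.

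**Scheduled time at the uncounted steps:** 3 steps × 4 weeks = 12 weeks; 12 / 72 = 16.7% of the treatment period, the same in both active arms. A participant restarted at 5 mg passes through the 5 and 7.5 mg steps again, so the affected time is longer for that participant.

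**Do other planned displays fill the gap?**
- SAP 4.6 and 4.6.2.1 include all events from first dose to the end of participation, and summarize treatment-emergent events by preferred term and arm. Events reported under Protocol 8.4 therefore reach those tables, placebo included.
- Protocol 6.4 treats intentional or repeated intake above 125% as significant noncompliance. SAP 6.2 defines compliance only by the 75% lower limit and plans no summary of excess intake.
- The optional listing in SAP 4.6.5.14 uses the same defined term, so it cannot be relied on to pick up the omitted events.

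**The case against.** The strongest defence is that the two rules serve different purposes. Protocol 8.4 tells sites what to report. SAP 4.6.5.14 defines an exposure-based analysis of tirzepatide: more than the maximum study dose, within an interval that matches the 72-hour spacing in the dosing instructions of Protocol 6.1. An analysis subset may be narrower than a collection rule, and a tirzepatide overdose on placebo is impossible by nature. This stands as a reason to keep the SAP count. It does not explain giving both events the same name, and neither document states the rationale.

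Three stronger readings are tempting, and the documents do not support them.

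- A reader might infer that double dosing in the first 12 weeks goes undetected. It does not: dose dates and times are recorded in the diary (Protocol 6.1), drug returns are counted (Protocol 6.4), and the event is reported as an adverse event (Protocol 8.4).
- A reader might infer that the safety report as a whole undercounts these events. It need not, because they enter the general treatment-emergent tables in every arm.
- A reader might infer that the SAP failed to declare a changed analysis in section 4.9. Protocol 9.4.4 plans no overdose analysis and does not list overdose among the events of special interest, so the silence of section 4.9 is not in itself a fault.

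The share of scheduled time is also not an estimate of impact. It shows when the rule cannot register a double injection, not how many such injections will occur.

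**Conclusion.** The inconsistency is real and minor. By the protocol's own definition, the SAP's overdose summary and listing are incomplete: they omit double injections at 2.5, 5 and 7.5 mg, which are the scheduled steps for the first 12 of 72 weeks (16.7%) in both active arms, and again after any restart at 5 mg. They also omit every extra placebo injection, so the placebo column is zero by construction. If the default Fisher's exact test of SAP 4.6 were applied to this table, the comparison with placebo would reflect the definition and not conduct in that arm.

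The gap is confined to those dedicated displays. No efficacy result, alpha allocation or power figure is touched. The number of events affected cannot be estimated from the documents. The conclusion assumes that sites report overdoses as Protocol 8.4 asks, and that participants follow the scheduled steps; dose interruptions would shift the affected weeks. It does not rest on any judgement about which definition is right.

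**What to change.** Reconcile Protocol 8.4 and SAP 4.6.5.14 by showing both events under separate labels:

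- Row (a): protocol-defined overdose, meaning more than the specified number of injections, for all arms including placebo.
- Row (b): more than 15 mg of tirzepatide in less than 72 hours, with a footnote that this cannot occur on placebo.

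Flag the listing in the same way, so that each entry shows which definition it meets. This keeps the SAP's count, ranks neither definition above the other, and changes no dose, clinical rule or data collection: overdose adverse events and dosing dates are already recorded. The cost is a sentence or two of SAP text, one extra table row and one listing flag.
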